**Footnotes for Flow Chart:**

1. Visit 1a is not required if a historical biopsy with sufficient and analysable material was collected within the last 6 months prior to randomisation (refer to [Section 3.3.1](#) and [5.1.1](#)).
2. Day of randomisation and the first administration of trial medication.
3. In case of early discontinuation (ED), Visit 32 should be completed instead of the planned treatment period visit, as soon as possible after trial medication is stopped. Liver biopsy should be performed at the ED visit providing the patient has been on treatment with trial medication for at least 40 weeks. MR imaging does not need to be performed at the ED visit if the patient discontinues before Visit 22 or if another MR imaging was performed within 12 weeks before the ED. [REDACTED] [REDACTED] [REDACTED] [REDACTED] Follow-up Visit 33 should be performed 4 weeks/28 days after the ED visit.
4. Number of weeks since randomization.
5. Trial visits will be conducted in two ways: 1/ at site (indicated by “S” in the [Flow Chart](#)) and 2/ remotely via telemedicine from patient’s home (indicated by “T” in the Flow Chart). Method of visit conduct (on-site or remote) can be modified. Modifications from an on-site to a remote visit require Sponsor approval.
6. Visit 1 can be conducted within less than 10 weeks of randomization. Before randomization, the Investigator should ensure that all safety laboratory results, ECG reading, imaging and liver biopsy results are available to ensure that the patient meets all inclusion criteria and does not meet any exclusion criteria. In the event of logistical issues with the reporting of results by the central vendor(s) a patient who meets all inclusion criteria and does not meet any exclusion criteria should be considered for participation in the clinical trial even if he/ she exceeds the screening period of 10 weeks. Extension of the screening period requires a Sponsor approval. If more than 12 weeks elapse from Visit 1 safety laboratory tests, ECG and vital signs should be repeated and results should be available before randomization.
7. Patient must be informed and written informed consent must be obtained prior to starting any trial procedure. Fasting is considered part of a trial procedure. For the historical biopsy, if applicable, a written non-trial specific informed consent has been obtained (per local standard).
8. Physical examination after screening is required only if patient reports symptoms.

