7. Known history of HIV (Human Immunodeficiency Virus) infection and/or tuberculosis and/or an acute COVID-19 infection at Visit 1 (confirmed by SARS CoV-2 RT-PCR test, see [Section 5.2.3](#)).
8. Abnormal laboratory values at Visit 1 as listed below:
  - a) Estimated Glomerular Filtration Rate (eGFR) < 45 mL/min/1.73 m^2 (Chronic Kidney Disease Epidemiology Collaboration [CKD-EPI] formula);
  - b) Platelet count < 150,000/μL (< 150x10^9/L);
  - c) Bilirubin level > 1.5x ULN (except for known Gilbert's syndrome with a conjugated bilirubin of < 0.3 mg/dL (< 5.13 μmol/L));
  - d) ALT and/or AST > 5x ULN;
  - e) Glycosylated haemoglobin (HbA1c) ≥ 9.5%;
  - f) Calcitonin ≥ 20pg/mL (≥ 5.84 pmol/L).
9. Diagnosis of a serious or unstable disease including hepatic (other than NASH), renal, gastroenterologic, respiratory, cardiovascular (including ischemic heart disease), endocrinologic, neurologic, psychiatric, immunologic, or hematologic disease and other conditions that, in the clinical judgment of the Investigator, are likely to interfere with the analyses of safety and efficacy in this trial. Patients with a history of organ transplantation except for corneal transplantation and patients with an expected life expectancy of less than 2 years are also excluded.
10. Any suicidal behavior or history of major depressive disorder requiring inpatient treatment or escalation of care in the past 2 years before randomization, any suicidal ideation of type 4 or 5 in the C-SSRS in the past 3 months prior to Visit 1.
11. Bariatric surgery, prior to or planned during trial conduct; except gastric-band surgery more than 2 years prior to screening (including adjustments) with a stable body weight within the last 12 months. Any other major surgery (major according to Investigator's assessment) performed within 12 weeks prior to randomization or planned during trial conduct.

12. Resting heart rate > 100 beats per minute (bpm) and/or blood pressure  $\geq$  160/ 95 mmHg at Visit 1. Blood pressure measurement should be repeated 10 minutes apart. Patient should be excluded only if the second measurement confirms a blood pressure  $\geq$  160/ 95 mmHg.
13. A marked prolongation of QT/ QTc (Fridericia) interval that is greater than 450 ms at Visit 1 or any other abnormal clinically significant ECG finding at Visit 1 (e.g., type 2 second-degree AV block (Type Mobitz II) or third-degree AV block).

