### 3.3.4.1 Discontinuation of trial treatment

An individual patient will discontinue trial treatment if:

- The patient wants to discontinue trial treatment, without the need to justify the decision.
- An AE (CTCAE Grade 3 or higher) occurred, and the AE was assessed by the Investigator as related to the trial treatment ([Section 5.2.6.1.6](#) and [5.2.6.1.7](#)).
- A clinically significant laboratory change or abnormality occurred and the Investigator judges to warrant discontinuation of trial treatment.
- The patient develops a sinus tachycardia (HR >120/min in two consecutive measurements 5 minutes apart and/or tachyarrhythmia (HR >110/min) or cardiac condition requiring medical intervention.
- Ventricular tachycardia is seen on ECG or syncope.
- Clinically relevant changes are seen on the ECG (QTcF prolongation >500 ms or an increase of 60 ms from baseline (Visit 2), or Type Mobitz II, or third-degree AV block, or Torsade de Pointes) or the patient develops any symptomatic AV block, atrial fibrillation or atrial flutter requiring medical intervention.
- The patient develops a clinically relevant coronary artery disease (e.g., CCS grading of Angina pectoris grade III-IV, or congestive heart failure NYHA class III-IV, or any major adverse cardiovascular event)
- Signs of suicidal behaviour or ideation are detected.
- The patient develops a malignant neoplasm.
- The patient experiences systemic hypersensitivity. Refer to [Section 4.2.1](#).
- The patient develops a clinically significant elevation of liver enzymes. Refer to [Section 10.1](#).
- The patient experiences an infection with SARS-CoV-2 (as confirmed by RT-PCR test) and presents with signs or symptoms requiring discontinuation of trial treatment as per Investigator's discretion.
- The patient has repeatedly shown to be non-compliant with important trial procedures and, in the opinion of both, the Investigator and Sponsor representative, is not willing or able to adhere to the trial requirements in the future.
- The patient needs to take concomitant medication that interferes with the trial treatment for more than 2 weeks. Refer to [Section 4.2.2.1](#) and [4.2.2.2](#).
- The patient experiences tolerance issues with the dose due to AEs over 2 weeks within the treatment period before Visit 14 ([Section 4.1.2](#)).
- The patient is out of compliance with trial medication (missing doses), please see [Section 4.3](#).

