### 5.2.3 Safety laboratory parameters

Safety laboratory parameters to be assessed are listed in [Table 5.2.3: 1](#). For the sampling time points please see the [Flow Chart](#). Patients do not have to be fasted for the blood sampling for the safety laboratory.

Analyses will be performed by a central laboratory; the respective reference ranges will be provided in the ISF. Instructions regarding sample collection, sample handling/ processing and sample shipping are provided in the laboratory manual.

The central laboratory will send reports to the Investigator. It is the responsibility of the Investigator to evaluate the laboratory reports. Clinically relevant abnormal findings as judged by the Investigator will be reported as AEs (please refer to [Section 5.2.6](#)).

In case the criteria for hepatic injury are fulfilled, a number of additional measures will be performed (please see [Section 5.2.6.1](#)) and the DILI Checklist provided in the ISF. The amount of blood taken from the patient concerned will be increased due to this additional sampling.

The central laboratory will transfer the laboratory data to the Sponsor periodically.

Table 5.2.3:1 Safety laboratory tests

Category	Test name
Haematology	Haematocrit Hemoglobin MCV (Mean Corpuscular Volume) MCH (Mean Corpuscular Haemoglobin) MCHC (Mean Cellular Haemoglobin Concentration) Red Blood Cell Distribution Width (RDW) Red Blood Cells (RBC) Count/ Erythrocytes WBC Count/ Leukocytes Platelet Count / Thrombocytes Differential Automatic (relative and absolute count): Neutrophils, Eosinophils, Basophils, Monocytes, Lymphocytes
Clinical chemistry	Albumin Alkaline phosphatase Amylase ALT (alanine aminotransaminase, SGPT) AST (aspartate aminotransaminase, SGOT) Bicarbonate Bilirubin total, fractionated if increased Calcium
Clinical chemistry	Chloride Creatinine Creatine kinase (CK) CK-MB, troponin (reflex tests if CK is elevated) Ferritin $\gamma$ -GT (gamma-glutamyl transferase) Glucose (plasma, not fasted) HbA1c/ Insulin/ C-Peptide** Lactate dehydrogenase (LDH) Lipase Magnesium Phosphate Serum Free Fatty Acids Potassium Protein total Sodium Urea (blood urea nitrogen, BUN) Uric acid Thyroid stimulating hormone (TSH)* Calcitonin* eGFR (CKD-EPI formula)
Coagulation	Activated Partial Thromboplastin Time (aPTT) Prothrombin Time (INR) Fibrinogen
Lipids	Cholesterol (total) HDL cholesterol LDL cholesterol (including VLDL) Triglycerides

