#### 5.2.6.1.4 Adverse events of special interest

The term adverse events of special interest (AESI) relates to any specific AE that has been identified at the project level as being of particular concern for prospective safety monitoring and safety assessment within this trial, e.g., the potential for AEs based on knowledge from other compounds in the same class. AESIs need to be reported to the Sponsor’s Pharmacovigilance Department within the same timeframe that applies to SAEs, please see [Section 5.2.6.2.2](#).

Hepatic injury is considered as AESI. It is defined by the following alterations of hepatic laboratory parameters as defined by the removal and stopping criteria in [Section 3.3.4.1](#). and [Section 10.1](#).

These laboratory findings constitute a hepatic injury alert and the patients showing these laboratory abnormalities need to be followed up according to the “DILI checklist” provided in the ISF.

In case of clinical symptoms of hepatic injury (icterus, unexplained encephalopathy, unexplained coagulopathy, right upper quadrant abdominal pain, etc.) without laboratory results (ALT, AST, total bilirubin) available, the Investigator should make sure these parameters are analysed, if necessary, in an unscheduled blood test. Should the results meet the criteria of hepatic injury alert, the procedures described in the DILI checklist should be followed.

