### Definition of baseline

In general, unless otherwise specified in the TSAP, the last non-missing measurement on or prior to the date of first dose of study treatment will be used as baseline for efficacy and safety variables.

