## 10. APPENDICES

### 10.1 REMOVAL OF INDIVIDUAL PATIENTS IN CASE OF INCREASED LIVER ENZYMES

Trial-specific procedures have been defined in case of increased liver enzymes after randomisation as outlined below.

- Normal aminotransferases at baseline

New elevations of aminotransferases to  $\geq 5x$  ULN (total bilirubin normal\* and no liver-related symptoms) should be followed by a repeat testing within 48 to 72 hours. If elevations persist, other causes of aminotransferase elevations should be evaluated along with tests of hepatic functions. If no other cause is identified, the patient should be monitored closely.

Treatment with trial medication should be discontinued if:

- ALT or AST increases to  $\geq 8x$  ULN
- ALT or AST increases to  $\geq 5x$  ULN for more than 2 weeks
- ALT or AST increases to  $\geq 3x$  ULN and the increase is accompanied by a concomitant increase in total bilirubin to  $\geq 2x$  ULN\*\* or INR to  $> 1.5$
- ALT or AST increases to  $\geq 3x$  ULN and the increase is accompanied by the appearance of fatigue, nausea, vomiting, right upper quadrant pain or tenderness, fever, rash, and/or eosinophilia ( $> 5\%$ )

- Abnormal aminotransferases at baseline

If a patient develops elevations of ALT or AST to  $\geq 3x$  baseline or  $\geq 300$  U/L (whichever is lower) with total bilirubin normal\* and no liver-related symptoms, the testing should be repeated within 48 to 72 hours. If elevations persist, then close observation (testing and physical examination 2 to 3 times a week) should be implemented, and discontinuation of trial medication should be considered. Decision to discontinue the trial medication should be considered based on factors that include how much higher than baseline ALT and AST values were relative to ULN and how much the on-treatment ALT and AST values have increased relative to baseline.

Treatment with trial medication should be discontinued if:

- baseline values were  $< 2x$  ULN, and ALT or AST increases to  $\geq 5x$  baseline values
- baseline values were  $\geq 2x$  ULN but  $\leq 5x$  ULN, and ALT or AST increases to  $\geq 3x$  baseline values
- ALT or AST increases  $\geq 2x$  baseline values or  $\geq 300$  U/L (whichever is lower) and the increase is accompanied by a concomitant increase in total bilirubin to  $\geq 2x$  ULN\*\* or INR concomitantly increases by  $> 0.2$  (to prevent false positive results, another sample should be tested within 24 hours)

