6.7 BASELINE, TIME WINDOWS AND CALCULATED VISITS

Definition of baseline

In general, baseline is defined as the last non-missing measurement on or prior to the first administration of study medication. In the case that the first dose of study medication is delayed beyond the date of randomisation, a post-randomisation value can be used as a baseline value provided that it meets the stated requirement.

Where clock times are available (expected to include laboratory safety data, 12-lead ECG, plasma Survodutide concentrations and biomarkers) they will be used in addition to dates to define baseline, since it is also expected that the time of first study drug administration will be accurately recorded on the eCRF for all patients.

Unscheduled and repeat assessments are eligible for use as baseline values provided that they meet the above criterion.

For 12-lead ECG, if a screening value needs to be used for baseline, it will be the average of all available triplicate screening ECG measurements (see [Section 5.4.1](#) for derivation details).

For vital signs, the baseline definition will make the additional requirement that the data records are pre-dose. In practice, this will also be done using the clock times as well as the date. A single pre-dose measurement is expected to be captured at the baseline visit (Visit 2), which will therefore be used as baseline. In any situation in which only a post-dose measurement is available at Visit 2 and no pre-dose measurements, Visit 2 will not be used as baseline; the screening visit (Visit 1) will be used as baseline instead.

For baseline NAS and fibrosis scores, the following specific considerations will be applied:

- Either a biopsy performed during the screening period or a historical biopsy (within 6 months) will be used to provide baseline data, without any further distinction made for analysis purposes between these two situations (both referred to subsequently as “screening biopsy”).
- The baseline value will be derived from central pathology readings of screening biopsy slides. For sites in all countries except China, central pathology screening readings will always be physical readings. For sites in China, central pathology screening readings may be digital readings, the handling of which is described below.
- All adequate central pathology readings which meet the baseline definition will be used, including any (expected to be occasional) readings performed by the back-up

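### If baseline is the last pre-dose value, Section 10.1 has no mandatory enzyme-only stop for a patient whose baseline ALT or AST is above 5x ULN

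*Protocol*

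**What the plan says.** Protocol 3.3.3, criterion 8, lists exclusions under "Abnormal laboratory values at Visit 1 as listed below". Item 8d is ALT and/or AST above 5x ULN.

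Visit 2 is the "Day of randomisation and the first administration of trial medication" (Flow Chart, footnote 2). Safety blood is drawn again at that visit, before dosing. Section 5.2.3 says of these samples: "Analyses will be performed by a central laboratory".

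For patients with abnormal aminotransferases at baseline, Section 10.1 gives two mandatory stops that depend on the enzymes alone:

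- baseline below 2x ULN: stop at ≥ 5x baseline;
- baseline from 2x to 5x ULN inclusive: stop at ≥ 3x baseline.

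Two further mandatory stops start at ≥ 2x baseline or ≥ 300 U/L, whichever is lower. They also need a rise in bilirubin or INR, or symptoms or eosinophilia. Below these sits a non-mandatory step at ≥ 3x baseline or ≥ 300 U/L, whichever is lower. If the elevation persists on retest, close observation "should be implemented, and discontinuation of trial medication should be considered". Section 10.1 adds that the decision should weigh how high the baseline was relative to ULN and how far the values have since risen.

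Section 10.1 does not say which visit supplies the baseline. The QTcF stop in 3.3.4.1 does: "an increase of 60 ms from baseline (Visit 2". The general definition in Protocol 7.2.1 is that "the last non-missing measurement on or prior to the date of first dose of study treatment will be used as baseline". SAP 6.7 follows the same rule and adds times of day to the dates: "Where clock times are available (expected to include laboratory safety data". SAP 7.8.2 tabulates a band for baseline ≥ 5x ULN with a later value above 2x baseline.

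**The concern.** The eligibility limit and the stopping bands both turn on 5x ULN, but they need not refer to the same blood sample. The limit applies at Visit 1, up to 10 weeks before the first dose and longer with sponsor approval. On the protocol's general definition, the stopping bands apply to a later sample on which no ALT or AST limit is set. A patient can pass the first and fall outside the second.

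For that patient, an isolated enzyme rise without a qualifying symptom, bilirubin change or INR change leads to a stop only through judgement. Patients with lower baselines have a fixed limit. The mandatory rule therefore runs out in the band where the liver is most abnormal at the start.

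**Working it through.** No sample size, power or type I error figure is involved, and the plan states no figure to reproduce. The check has four steps.

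**1. Can an eligible patient have a baseline above 5x ULN?**

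- Criterion 8d applies at Visit 1 only.
- Laboratory tests must be repeated before randomisation only if more than 12 weeks have passed since Visit 1 (Flow Chart, footnote 6; Section 6.2.1).
- The Visit 2 sample is drawn on the day of first dosing and sent to a central laboratory. Nothing ties 8d to it.
- Protocol 7.2.1 and SAP 6.7 make that sample the baseline. In its vital-signs paragraph, SAP 6.7 also treats Visit 2 as the baseline visit.

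On that definition the answer is yes. If 10.1 means the Visit 1 value, 8d caps baseline at 5x ULN and the bands cover every eligible patient.

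**2. Mandatory enzyme-only stop by abnormal baseline (in multiples of ULN)**

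| Baseline | Rule in 10.1 | Stop |
|---|---|---|
| 1.5 | 5 × 1.5 | 7.5 |
| 1.99 | 5 × 1.99 | 9.95 |
| 2.0 | 3 × 2.0 | 6.0 |
| 4.9 | 3 × 4.9 | 14.7 |
| 5.0 | 3 × 5.0 | 15.0 |
| 5.1 | none | none |
| 8.0 | none | none |

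**3. Where the remaining numeric steps start, at a baseline of 5.1x ULN**

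The documents give no ULN, so I assume 30 to 60 U/L. Baseline is 5.1 × ULN. Both 3x baseline (at least 459 U/L) and 2x baseline (at least 306 U/L) exceed 300 U/L throughout this range. The 300 U/L limit therefore governs the observation step and also the bilirubin/INR and symptom stops.

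| Assumed ULN (U/L) | Baseline (U/L) | 300 U/L as a multiple of baseline |
|---|---|---|
| 30 | 153 | 1.96 |
| 40 | 204 | 1.47 |
| 55 | 280.5 | 1.07 |
| 60 | 306 | 0.98 (already exceeded) |

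Close observation would therefore start early in this band. What is missing is the level at which stopping becomes mandatory.

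**4. What a completed top band would give, at a baseline of 5.1x ULN**

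- Extending the existing 3x-baseline rule: 3 × 5.1 = 15.3x ULN (612 U/L at an assumed ULN of 40).
- Using the 2x-baseline level that SAP 7.8.2 tabulates: 2 × 5.1 = 10.2x ULN (408 U/L at an assumed ULN of 40).

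The two documents also differ at the boundary. The protocol's middle band includes 5.0x ULN and stops at ≥ 3x baseline. The SAP's middle band ends below 5x ULN and uses > 3x baseline. A baseline of exactly 5.0x ULN is therefore in the 3x band in the protocol and the 2x band in the SAP.

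**The case against.** The strongest objection is that the baseline definition in Protocol 7.2.1 and SAP 6.7 is written for analysis and not for investigators. The upper band in 10.1 ends exactly where criterion 8d begins, which suggests that the drafters had the eligibility value in mind. That is a fair reading, and under it there is no gap. But 10.1 does not say so, and the only written definition points to the last pre-dose value.

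Nor are patients above 5x ULN unprotected, though a reader might infer that. The retest and observation step applies to them, with examination and testing two to three times a week, and 10.1 guides the decision to stop. The symptom stop includes nausea, reported in up to 70% of patients on drug in the multiple rising dose trial (Protocol 1.2). Section 3.3.4.1 requires a stop for a related adverse event of Grade 3 or higher, or for a laboratory change that the investigator judges to warrant it. The DMC receives cases of drug-induced liver injury (Section 8.7). Eligibility is reviewed again at Visit 2. If only one enzyme exceeds 5x ULN, the other may still fall in a lower band. All of this stands, and it limits the gap to an isolated enzyme rise.

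A reader might also infer that the hepatic-injury AESI shares the gap. Section 5.2.6.1.4 defines it by "alterations of hepatic laboratory parameters as defined by the removal and stopping criteria". If that means only the mandatory stops, it does. But the whole of 10.1 is headed as removal of patients, so the phrase may also take in the step at ≥ 3x baseline or ≥ 300 U/L, which would then be a numeric trigger. The documents do not settle this.

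Finally, a large effect of the unnamed visit inside the bands is tempting to claim. Visit 1 at 1.9x and Visit 2 at 2.1x ULN give stops of 5 × 1.9 = 9.5x and 3 × 2.1 = 6.3x ULN, about 1.5-fold apart. Most of that is the rule's own step at 2x ULN, which remains whichever visit is named.

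**Conclusion.** The point holds in conditional form. If baseline is the last value before the first dose, 10.1 has no mandatory enzyme-only stop above 5x ULN, and criterion 8d does not prevent such a baseline. If baseline is the Visit 1 value, there is no gap.

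The effect is small. The documents give no rate at which patients cross 5x ULN between the two visits, so the number affected cannot be derived; it is probably low. The SAP row for baseline ≥ 5x ULN does not show that higher values were expected, because exactly 5.0x ULN is eligible. It does show that the analysis has a top band with no matching stop. The log for Global Amendment 3 attributes the revision of 10.1 to consensus guidelines that cannot be consulted here, so whether the upper bound is deliberate cannot be judged.

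This is a minor point and a cheap improvement.

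**What to change.** 1. In Section 10.1, state that baseline is the last value before the first dose, normally Visit 2.
2. In Section 10.1, close the top band in one of two ways. Either delete the 5x ULN upper bound, so that any baseline of 2x ULN or more stops at ≥ 3x baseline, which continues the existing rule without a drop. Or add a stop for baselines above 5x ULN at the > 2x baseline level that the SAP already tabulates, which is stricter and lowers the limit just above 5x ULN.
3. In SAP 7.8.2, align the bands and operators with the rule chosen, so that the table counts the patients the rule would stop.

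Naming Visit 1 as baseline would also remove the gap, but 10.1 would then depart from the general definition in Protocol 7.2.1 and SAP 6.7.

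The cost is one sentence and one deletion or added line in 10.1, plus an aligned row in the SAP. The downside is possibly a few more treatment stops.
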